Breast cancer-related lymphedema (BCRL) remains a burdensome and much feared complication of breast cancer treatment. BCRL may occur after lymph node surgery or radiation to the axillary regions, interrupting the proper circulation of lymph fluid. This protein-rich fluid then accumulates in the interstitial tissues of the arm, shoulder, or hand, and/or the breast or trunk, causing swelling that characterizes this condition.[1] Patients may experience a range of symptoms, including heaviness, pain, tightness, changes in skin quality, decreased range of motion, as well as a higher risk for infection in the affected area(s). The morbidity resulting from BCRL is significant and negatively impacts almost all aspects of patients' lives, contributing to anxiety and even depression.[2-7]

Risk factors that have been well established in the literature include axillary lymph node dissection (ALND), regional lymph node radiation (RLNR), number of pathologically involved lymph nodes, and high Body Mass Index (BMI).[8-13] Sentinel lymph node biopsy (SLNB) is favorable to ALND for the axillary staging of early disease because it significantly decreases the risk for BCRL, although the risk is not entirely eliminated.[8,12,14,15] In recent analyses by our team looking at data from over 2,171 women, stratified by BC treatment received, the 5-year point estimate of BCRL was 31.2% after ALND and RLNR, 24.6% after ALND without RLNR, 12.2% after SLNB and RLNR and 8.3% after SLNB without RLNR.[16]

Role of Injections in Lymphedema Risk

As the prevention of lymphedema is preferable to an impairmentbased approach, patients treated for BC historically received advice regarding precautionary behaviors and lifestyle modifications (e.g. avoiding injections) they can adopt, in theory, to reduce their life-long risk of developing this condition, many of which remain unsubstantiated by highlevel, scientific support.[17,18]

Given the paucity of evidential support and controversy surrounding these measures, our team conducted a literature review[18] and two

prospective analyses[19,20] to assess whether lifestyle risk exposures, including injections on the ipsilateral arm, conferred a risk for the development of lymphedema. By multivariate analysis in both prospective

studies (n=632 and n=327), injections were not associated with an increase in arm volume.

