In our literature review in The Lancet Oncology,[18] we looked at 85 manuscripts to determine whether historical literature has found a tangible association between presumed risk-increasing behavioral exposures (including ipsilateral skin puncture, cellulitis infections) and BCRL. We found that over the past several decades, the majority of published studies have demonstrated that the clinical benefit of current precautionary guidelines has not been established. Among 31 original studies examining the association between these exposures and BCRL, only eight are prospective cohort studies.[10,19,21–24] Among these, four studies demonstrate a significant correlation between lymphedema and commonly reported lifestyle-based risk factors, in one case, skin puncture.[24] The study that found a correlation between skin puncture and lymphedema was composed only of patients with ALND (n=188), and based on 8 patients who developed lymphedema after skin puncture.

In summary, skin puncture is not associated with increased arm volume based on available evidence.

COVID-19 Vaccine and Lymphedema Risk

Lymph node swelling is a known and common side effect of both the Moderna and Pfizer COVID-19 vaccines. This is the body's normal reaction to the vaccine. According to the Centers for Disease Control and Prevention, axillary swelling or tenderness (i.e., lymphadenopathy) was a solicited adverse event reported in 11.6% of patients (vs 5.0% for placebo) following dose 1 and 16.0% of patients (vs 4.3% for placebo) following dose 2 after the Moderna vaccine.[25] This occurred in the arm and neck 2-4 days following vaccination with a median duration of 1-2 days. After the PfizerBioNTech COVID-19 vaccine, lymphadenopathy was reported as an unsolicited adverse event with 58 more cases in the vaccine group than the placebo group (64 vs 6 respectively). This occurred in the arm and neck within 2-4 days of vaccination and lasted for a mean of 10 days.[26] Rates and duration of adenopathy in both trials were based on clinical assessment (i.e., physical examination). Anecdotally, mammographically detectable axillary adenopathy following COVID-19 vaccinations has been unilateral.[27]

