It is worrisome that lymph node swelling after the vaccine mimics that found in breast cancer which has spread to the lymph nodes. This side effect will cause worry and anxiety amongst patients as a result. For patients who have had lymph node removal (ALND or SLNB) and are at risk of lymphedema, we are concerned that the lymph node swelling may tax the lymphatic system and incite lymphedema in those at risk or worsen it in those with BCRL. Fear of lymphedema is high in this population and we need to better understand what risk, if any, lymphadenopathy after the COVID-19 vaccine imparts to BCRL risk.

Although our previous research has found that injections were not associated with increased arm volume[18,19,28], the COVID-19 vaccine is new. We do not know how lymph node swelling associated with the vaccine will affect patients at risk for or suffering from lymphedema. We cannot therefore apply the results from our previous studies to our recommendations for patients around the COVID-19 vaccine.

It is imperative to educate patients about vaccine options, such as receiving the vaccine in an alternative location such as the anterolateral thigh. It is imperative that we study patient experiences, choices, side effects and lymphedema incidence after the COVID-19 vaccine.

Study Summary and Clinical Implications

This study will be a prospective, longitudinal cohort study incorporating patient-reported surveys after vaccine receipt. Given that the COVID-19 vaccine will likely be required in the long term, this data will inform patient recommendations for those receiving the COVID-19 vaccine who are at risk for and with lymphedema.

RESEARCH DESIGN AND METHODS

Briefly describe study design and anticipated enrollment, i.e., number of subjects to be enrolled by researchers study-wide and by Partners researchers. Provide a brief summary of the eligibility criteria (for example, age range, gender, medical condition). Include any local site restrictions, for example, “Enrollment at Partners will be limited to adults although the sponsor’s protocol is open to both children and adults.”

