This is a prospective, longitudinal observational cohort study incorporating patient-reported surveys before and/or after vaccine receipt. Female patients who are ≥ 18 years of age and have a history of breast cancer will be eligible. For the MGH site, patients must have received some breast cancer treatment at MGH or its affiliates and received perometry measurements to measure arm volume to be eligible for this study. Per our MGH lymphedema screening records, there are a minimum of 4,947 patients who will qualify for this study. Based on an anticipated survey response of 20%, we anticipate minimal accrual at MGH to be approximately 989 patients.

Briefly describe study procedures. Include any local site restrictions, for example, “Subjects enrolled at Partners will not participate in the pharmacokinetic portion of the study.” Describe study endpoints.

REDCap was used to develop surveys to be sent electronically to patients. We will use the surveys to elicit patient choices around receiving/not receiving the vaccine, injection site of choice and side effects. Complete versions of all survey involved in this study have been attached to this application, but not all questions will be relevant to each patient. Therefore, branching logic is built into our REDCap database to ensure patients only

have to answer the questions that are relevant to them. For example, a patient who receives a COVID-19 vaccine that only has one dose will not need to fill out symptoms information for their second dose as it is not applicable to them.

For all eligible patients from MGH who use MGB Patient Gateway, they will be sent a recruitment letter via MGB Patient Gateway with a REDCap survey link embedded. We have been working with the Partners eCare team to build this recruitment report.

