on how best to share our data (perhaps by applying for a data use agreement). Therefore, we will send an additional letter through Patient Gateway to these participants explaining why we would specifically appreciate their participation in the study, signed by the CANVAX PI. These participants have not opted out of being contacted for future research. The Lymphedema Research Program Clinical Research Coordinators are listed as Research Assistants on the CANVAX protocol. If a CANVAX patient is seen in the Breast Cancer Center for routine follow ups or arm measurements, CRCs will offer to have the patient fill out the survey during the visit. Depending on response rate from the Patient Gateway letter, CRCs may also call these patients (a script is attached) unless they decline to participate.

If the participant consents, they will immediately begin a survey asking for information about their first dose and symptoms and second dose and symptoms, if applicable. For participants who have had all doses of their respective vaccines, their participation is complete after responding to a survey about all applicable doses. For participants who have had one dose of their vaccine and plan to have a second, they will fill out the expected date of their second dose and told that the invitation will be resent on that date via Patient Gateway for them to fill out a second survey on that dose. A second link will be available in the recruitment letter directing participants to fill out experiences with the booster dose of the vaccine if they receive it. Copies of both surveys (first/second dose experience and booster dose experience) are attached.

[figure not shown]

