Upon completion of the survey study, we may apply for secondary use of data from our Screening Program to analyze perometry and clinicopathological data for participants who have responded to surveys regarding their COVID-19 vaccinations and who are established participants in our MGH Breast Cancer-Related Lymphedema Screening Program (2008P000540 and 1999P009256). We have applied for and been granted secondary use under Insight number 2021P003414. This program routinely screens patients starting at pre-operative baseline, throughout and beyond treatment at their oncology follow-up visits. Screening consists of perometry measurements, a valid and reliable measure of arm volume used for lymphedema screening[29], as well as a patient-reported outcome measure, the Symptoms Experience Index (SEI), a validated measure of symptoms after breast cancer surgery. Analysis of this data will inform BCRL risk after COVID-19 vaccination versus that from our historical control data.

For studies involving treatment or diagnosis, provide information about standard of care at Partners (e.g., BWH, MGH) and indicate how the study procedures differ from standard care. Provide information on available alternative treatments, procedures, or methods of diagnosis.

Not applicable: this study does not involve treatment or diagnosis.

Describe how risks to subjects are minimized, for example, by using procedures which are consistent with sound research design and which do not unnecessarily expose subjects to risk or by using procedures already being performed on the subject for diagnostic or treatment purposes.

The surveys sent, the main research components of this study, do not present risk to patients. We will protect patients by inviting the majority of the study participants through secure Patient Gateway contact. All surveys will be completed in REDCap and all survey responses will be stored in our secure REDCap database. All patients who are offered to participate in this study are already familiar with the MGH Lymphedema Research Program.

Describe explicitly the methods for ensuring the safety of subjects. Provide objective criteria for removing a subject from the study, for example, objective criteria for worsening disease/lack of improvement and/or unacceptable adverse events. The inclusion of objective drop criteria is especially important in studies designed with placebo control groups.

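### Models for local arm, axillary and breast side effects test cancer-treatment predictors without any pre-dose symptom or lymphedema value

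*Combined protocol and SAP*

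**What the plan says.** All places are in the combined protocol and SAP.

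- **Survey timing.** The Study Summary and Clinical Implications paragraph describes a cohort "incorporating patient-reported surveys after vaccine receipt". The opening of Research Design and Methods says "incorporating patient-reported surveys before and/or after vaccine receipt". The study procedures describe only questions tied to a dose: on consenting, women are told "they will immediately begin a survey asking for information about their first dose and symptoms and second dose and symptoms, if applicable". For women who have had every dose, "their participation is complete after responding to a survey about all applicable doses", so they answer once, looking back.
- **Survey content.** "Complete versions of all survey involved in this study have been attached to this application", but the forms are not in the available text.
- **Background symptoms.** The Background section says of breast cancer-related lymphedema: "Patients may experience a range of symptoms, including heaviness, pain, tightness, changes in skin quality, decreased range of motion". It names axillary dissection and regional nodal radiation as risk factors.
- **Models.** The Statistical Methods fit one logistic model per side effect across all doses, with a random effect for participant. Candidate predictors are age, BMI, surgery type, axillary surgery, radiation and chemotherapy. Any coefficient with p below 0.05 is declared a predictor. No pre-dose symptom or prior-lymphedema term is listed.
- **Data held elsewhere.** The screening programme collects perometry and "the Symptoms Experience Index (SEI), a validated measure of symptoms after breast cancer surgery", starting before surgery. The stated purpose of analysing those data is to assess lymphedema risk, not to adjust the side-effect models.

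**The concern.** For a local symptom such as arm pain or tightness, axillary dissection or radiation can raise the reported frequency in two ways: by changing the reaction to the vaccine, or by leaving a chronic symptom that the woman reports when asked about her dose. The models have no variable that separates the two. The random effect handles correlation between a woman's answers for different doses. It does not remove a persistent difference between treatment groups, and a chronic symptom can be reported again at each dose.

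The study is meant to inform recommendations for women at risk of, or living with, lymphedema. A finding that dissection or radiation predicts a local vaccine reaction, when it reflects symptoms already present, would mislead the group that the protocol describes as fearful of lymphedema.

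**Working it through.** **1. The plan's own figure.** Accrual: 4,947 × 0.20 = 989.4, against the stated figure of about 989. It reproduces. No power calculation or expected odds ratio is given, so there is no planned effect to check.

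**2. How a false association arises.** All inputs in this step are assumptions. Let c be the chronic-symptom prevalence (10% without axillary surgery, 30% after dissection), v = 15% the vaccine-caused probability in both groups, and f the share of chronic symptoms reported as side effects.

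P(report) = 1 − (1 − f·c)(1 − v); odds ratio = odds after dissection ÷ odds without axillary surgery.

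| f | No axillary surgery | Dissection | Odds ratio |
|---|---|---|---|
| 0% | 15.0% | 15.0% | 1.00 |
| 10% | 1 − 0.990 × 0.85 = 15.9% | 1 − 0.970 × 0.85 = 17.6% | 1.13 |
| 25% | 1 − 0.975 × 0.85 = 17.1% | 1 − 0.925 × 0.85 = 21.4% | 1.32 |
| 50% | 1 − 0.950 × 0.85 = 19.3% | 1 − 0.850 × 0.85 = 27.8% | 1.61 |
| 100% | 1 − 0.900 × 0.85 = 23.5% | 1 − 0.700 × 0.85 = 40.5% | 2.22 |

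**3. Smaller gaps.** Take a local symptom reported by 11.6% in the reference group, 5.0% of it background. These levels are borrowed from the dose-1 node-swelling figures only as a starting point. Then v = 1 − (1 − 0.116)/(1 − 0.05) = 0.0695.

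- Background 2 points higher in the exposed group: 1 − 0.9305 × 0.93 = 13.5%, odds ratio 1.19.
- Background 5 points higher: 1 − 0.9305 × 0.90 = 16.3%, odds ratio 1.48.

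With 989 women, 10% to 50% of them exposed (assumed), one dose, no covariates and a two-sided 0.05 test (sidedness is not stated), the chance of a false p < 0.05 is 9–14% for the 2-point gap and 29–56% for the 5-point gap.

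**4. Does conditioning on the pre-dose symptom remove it?** In the illustration at f = 50%, women without the chronic symptom report at 15% in both groups. Women with it report at 1 − 0.50 × 0.85 = 57.5% in both groups. The odds ratio is 1.0 in each stratum. The strata recombine to the table: 0.10 × 57.5% + 0.90 × 15% = 19.3%, and 0.30 × 57.5% + 0.70 × 15% = 27.8%. This assumes that the pre-dose symptom is measured without error.

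**5. Node swelling.** The Background gives the Moderna trial rates as "11.6% of patients (vs 5.0% for placebo) following dose 1 and 16.0% of patients (vs 4.3% for placebo) following dose 2". Placebo reports equal 5.0/11.6 = 43% and 4.3/16.0 = 27% of the vaccine-arm rates. This shows that such reports occur without vaccine. It says nothing about chronic post-treatment symptoms.

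**The case against.** The strongest reply is that the survey forms cannot be seen. The protocol says that the surveys elicit side effects, and the Statistical Methods report a median duration for them. Both suggest that women were asked about time-limited reactions, not about every symptom they have. If the items ask for new or worsened symptoms, most of the bias goes. This stands, and the point is conditional on it. Even so, looking back and attributing a symptom to a dose is not the same as a measured baseline.

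Overlap with the outcomes is also not established. The Statistical Methods name only lymph node swelling, which is not among the chronic symptoms listed in the Background. This stands too, so the point is confined to local side effects that do overlap.

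Injection site is collected, and the first hypothesis expects most women to choose the untreated side. Laterality could therefore help to separate a reaction from a treated-side symptom. That is fair, but the models list no laterality term.

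Three stronger readings are tempting, and the documents do not support them:

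- A reader might infer that symptoms were asked about only after vaccination. One design statement allows surveys beforehand, so all that can be said is that no pre-dose symptom survey is described.
- A reader might take 43% and 27% as the share of reports due to chronic symptoms. They come from placebo injections in a vaccine trial, and a pre-dose symptom score would not remove such reports.
- A reader might infer that crude rates are presented as vaccine-caused. The documents do not say so; the second hypothesis compares node swelling with the general-population rate.

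**Conclusion.** The point holds for local arm, axillary and breast side effects, and only if the survey items do not already restrict answers to new or worsened symptoms. In that case the coefficients for axillary surgery, surgery type and radiation can be biased upward, and nothing in the planned models corrects this. Systemic side effects such as fever are largely untouched.

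The size is unknown. The odds ratios of 1.3 to 2.2 rest wholly on the assumed 10% and 30% prevalences, the 15% vaccine effect and misreporting of 25% to 100%. They fall to 1.13 at 10% misreporting and to 1.0 at none. They are not estimates for this study. The three statements on survey timing differ and should be reconciled.

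**What to change.** 1. State in the Statistical Methods whether each local item asked for symptoms that were new or worse since the dose, and reconcile the survey-timing statements.
2. For side effects that overlap Symptoms Experience Index (SEI) items, add each woman's last pre-dose value of that item as a covariate. Where it is missing, or not covered by the secondary-use grant, use pre-dose lymphedema status from perometry.
3. As a sensitivity analysis, repeat each of these models in women without that symptom before the dose.
4. For node swelling, show the placebo rates quoted in the Background beside the observed frequency, as context for background reporting and not as evidence of chronic symptoms.

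**Cost.** Data linkage and a few extra model runs, with no new patient contact. Since the Statistical Methods are written in the past tense, this is likely to be a supplementary analysis. The secondary-use text names perometry and clinical-pathological data but not the SEI, so coverage must be confirmed. The SEI items are not listed either, so overlap must be checked. Eligibility requires perometry, not an SEI. Some women will therefore have an old or missing pre-dose value and drop out of the sensitivity analysis, which may favour regular clinic attenders. Report how many are lost and how old the values used are.

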The invitation to participate was previously resent a second time after 72 hours with no response, and then a third time at seven days after initial contact (prior to new IRB regulations regarding reminders). An updated version of the recruitment letter was sent with the booster survey once this dose becomes available. The letter includes a new second survey link to questions about the booster vaccine. It is stated in the recruitment letter that this is an updated version of the study which makes the survey more user friendly and includes the booster dose. For this reason, all participants will receive the invitation to participate unless they have specifically asked not to be contacted about our study again. A follow up phone call may be made if we do not hear back in 2 weeks. For patients who do not complete the surveys after consenting to participate (either due to forgetting to finish the surveys or having technical difficulties finding the surveys), the Clinical Research Coordinator will call the participant at the phone number in the EPIC chart to assist in completing all surveys. A telephone script is attached.

Since booster doses of all vaccines are recommended by health officials at differing times, we will contact participants securely through Patient Gateway who have already completed survey(s) about their 1st/2nd doses asking them to complete the booster survey as well. This updated booster letter will include information regarding optional arm measurements as well. This states that we would like participants to make appointments for arm measurements 1-2 weeks before the booster, 7-14 days after the booster, 4-6 weeks after the booster, and 3 months after the booster, +/- 2 weeks. This is an optional component of participation in this study. The letter will be sent through patient gateway. The letter will be sent again to participants who have completed surveys about their 1st/2nd doses in March of 2022 as we anticipate many more responses now as the booster had become more widespread. Depending on response rates, we may reach out by phone, using the attached letter as a script, to help participants complete the booster survey.

98 participants are eligible for our study as well as the CANVAX: Cancer, COVID and Vaccination study (2021P000746). We have been collaborating with the CANVAX team and would like for as many participants as possible of these 98 to complete both studies. In the future, both teams will collaborate

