Additionally, we will reach out to participants through Patient Gateway who have consented to the study and experienced some form of swelling and provide them with contact information if they would like to schedule arm measurements before and/or after receiving the booster vaccination. All participants are aware that arm measurements remain available to them as they have in the past. Language for this letter is attached. We will resend an updated letter to participants who reported lymph node swelling after any of the three doses. The updated language is attached. As has been conducted with the booster arm measurements, parking will be compensated for those coming in for additional appointments outside of regular oncology visits. Depending on response rates, we may also reach out to participants by phone using the attached letter as a script.

An additional survey asking questions about prior SARS-CoV-2 infection will be sent to all participants who have consented to participate through answering questions on any doses of the vaccine. The CANVAX study recently published results that prior infection was associated with higher systemic, but not local, symptoms⁴³. We would like to test this in our population and therefore must collect data on any prior infections to

compare with the data we have on vaccine experiences. The invitation to complete this survey, attached, will be sent securely through patient gateway, and we may reach out by phone depending on response rates at the discretion of the PI. A consent addendum is included in the survey language, attached. No new subjects will be enrolled through this survey.

Participants will be aware (explained in consent fact sheet) that we may review their medical records for the purposes of this study and that we will analyze their survey data in conjunction with their breast cancer treatment information and lymphedema screening data.

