Given minimal risk to patients and the fact that it is an observational study, the main criteria for removing a subject from the study would be patient withdrawal from the study.

FORESEEABLE RISKS AND DISCOMFORTS

Provide a brief description of any foreseeable risks and discomforts to subjects. Include those related to drugs/devices/procedures being studied and/or administered/Performed solely for research purposes. In addition, include psychosocial risks, and risks related to privacy and confidentiality. When applicable, describe risks to a developing fetus or nursing infant.

Psychosocial risks may include frustration associated with receiving survey prompts as to whether the patient has received the first dose of the COVID19 vaccine, given this is an emotional topic currently. There could also be distress associated with the potential for the known side effect of lymph node swelling after receiving the COVID-19 vaccine in patients at risk for lymphedema.

EXPECTED BENEFITS

Describe both the expected benefits to individual subjects participating in the research and the importance of the knowledge that may reasonably be expected to result from the study. Provide a brief, realistic summary of potential benefits to subjects, for example, "It is hoped that the treatment will result in a partial reduction in tumor size in at least 25% of the enrolled subjects." Indicate how the results of the study will benefit future patients with the disease/condition being studied and/or society, e.g., through increased knowledge of human physiology or behavior, improved safety, or technological advances.

Benefits to society would include wide distribution of important patient education regarding the side effects and recommendations for safe receipt of the COVID-19 vaccine. This will minimize distress in our patients who experience a potentially alarming symptom such as lymph node swelling, which may concern patients who underwent lymph node removal. Since we

will be monitoring for symptoms, we will be able to direct patients to seek medical care in the event lymph node swelling symptoms persists to six weeks after the second dose. If there is clinical concern that persists ≥ 6 weeks after the final vaccine dose, axillary ultrasound is recommended per current MGH Breast Imaging standard of care. There are no direct benefits to patients who do not experience lymph node swelling.

EQUITABLE SELECTION OF SUBJECTS

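### Between-dose enrollees are invited to the dose-2 survey on the expected dose-2 date, before the stated Moderna swelling onset, and nothing re-asks early responders or checks response timing

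*Combined protocol and SAP*

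**What the plan says.** **Survey timing.** Under Research Design and Methods (study procedures), a participant who has had one dose and plans a second is handled as follows: "they will fill out the expected date of their second dose". Such participants are then "told that the invitation will be resent on that date via Patient Gateway for them to fill out a second survey on that dose". People who have already had all their doses report them in one survey at enrolment.

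**Stated course of swelling.** The background section on the COVID-19 vaccine and lymphedema risk says of Moderna: "This occurred in the arm and neck 2-4 days following vaccination with a median duration of 1-2 days". For Pfizer-BioNTech the wording is "within 2-4 days of vaccination and lasted for a mean of 10 days". The Moderna frequencies are "11.6% of patients (vs 5.0% for placebo) following dose 1 and 16.0% of patients (vs 4.3% for placebo) following dose 2".

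**Repeat contact.** The 72-hour and seven-day resends, and the possible call at two weeks, are for people who have not responded. A further call is for people who consented but did not finish. With the updated letter that added the booster survey, "all participants will receive the invitation to participate unless they have specifically asked not to be contacted about our study again". Nothing says that a dose-2 answer already given was asked for again or replaced.

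**Analysis.** The Statistical Methods report the frequency and median duration of side effects for each mRNA dose. They fit a logistic model per side effect across doses, with participant random effects, and compare side-effect profiles across three doses. The listed predictors are age, BMI, surgery type, axillary surgery, radiation and chemotherapy. Time from dose to response and effects still present at response are not mentioned.

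**The concern.** The dose-2 invitation for this group is sent on day 0 of a planned date. A person who answers that day or the next has not reached day 2, the earliest onset stated for Moderna. If the dose is postponed, the invitation precedes the dose itself. An early answer of no swelling looks complete and would enter the analysis as a true negative. Swelling that has begun but not ended when the survey is answered has no final duration. With a mean of 10 days for Pfizer, that could affect answers well beyond the first few days.

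Dose-2 swelling enters the per-dose frequencies, the median durations and the comparison across doses. It also bears on Hypothesis 2 (same rate as the general population) and on the exposure in Hypothesis 3 (swelling as a possible risk factor for lymphedema).

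**Working it through.** **The plan's own planning figure.** 4,947 eligible x 20% response = 989.4, which reproduces the stated 989. This is anticipated minimum accrual, not a count of dose-2 reports, and is used below only to set a scale.

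**Inputs from the documents.** Moderna swelling 11.6% after dose 1 and 16.0% after dose 2; onset on days 2-4; median duration 1-2 days (Moderna) or mean 10 days (Pfizer). Reference difference = 16.0 - 11.6 = 4.4 points. Odds ratio (OR) = (0.16/0.84)/(0.116/0.884) = 1.45.

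**Assumptions, not in the documents.** Dose 2 is given on the expected date. Onset is uniform over days 2-4. Response delay after the invitation is exponential with median m = 1, 3 or 7 days. Any answer after onset records the swelling. The group supplies a share f of dose-2 reports.

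**Step 1: fraction of swelling captured.** c(m) = mean of 2^(-t/m) over t from 2 to 4 days, giving 0.135, 0.504 and 0.744 for m = 1, 3 and 7.

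**Step 2: observed dose-2 rate.** Rate = 16.0% x [1 - f(1 - c)]. The difference and OR below are against a dose-1 rate left at 11.6%, that is, with dose-1 reports taken as complete.

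| Share f | Observed dose-2 rate, % (m = 1 / 3 / 7) | Difference, points | OR |
|---|---|---|---|
| 5% | 15.3 / 15.6 / 15.8 | 3.7 / 4.0 / 4.2 | 1.38 / 1.41 / 1.43 |
| 10% | 14.6 / 15.2 / 15.6 | 3.0 / 3.6 / 4.0 | 1.30 / 1.37 / 1.41 |
| 25% | 12.5 / 14.0 / 15.0 | 0.9 / 2.4 / 3.4 | 1.09 / 1.24 / 1.34 |

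The difference and OR columns are the worst case with respect to dose-1 completeness.

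**Step 3: the same loss at dose 1.** If dose-1 reports lose the same fraction, the difference is 4.4 x [1 - f(1 - c)]. At f = 10% and m = 1 the rates are 14.6% and 10.6%, a difference of 4.0 points and an OR of 1.44, against 3.0 and 1.30 in the table. With half that loss at dose 1 the difference is about 3.5 points. At f = 25% and m = 1, equal loss gives 4.4 x 0.784 = 3.4 points, against 0.9.

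**Step 4: later replacement.** If the updated invitation replaced half of the missed dose-2 reports, the loss halves. With dose 1 complete, the differences become 3.7, 4.0 and 4.2 points at a 10% share. If all were replaced, no bias remains.

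**Step 5: comparison with sampling error.** Half-width = 1.96 x sqrt(0.16 x 0.84/N) = 2.3 points at N = 989 and 3.2 points at an assumed N = 500. The bias in the dose-2 rate is 0.2-1.4 points at f = 5-10%. It reaches the half-width at f = half-width/[0.16(1 - c)], which is 17%, 29% or 56% at 989 reports and 23%, 41% or 79% at 500.

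**Step 6: duration.** With exponential durations, the fraction of episodes resolved by day d is the mean over onset o of 1 - exp(-(d - o)/mean). For a mean of 10 days this is 33% by day 7, 67% by day 14 and 92% by day 28. For a median of 2 or 1 days it is 75% or 93% by day 7.

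**The case against.** The strongest reply is that the protocol fixes when the invitation goes out, not when it is answered. Only people enrolled between doses who answer early are exposed, and nothing suggests that they are numerous. The survey forms are attachments that are not reproduced, and they may ask for actual dose dates, symptom dates or ongoing symptoms. The updated invitation may have produced later dose-2 reports. REDCap data are also reviewed every 8 weeks under Monitoring and Quality Assurance. Most of this stands and limits the size. It does not remove the gap: the reminders do not reach someone who has already answered, no replacement rule is stated, and a general review for accuracy and completeness would not flag a premature negative.

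A reader might infer that early answers must shrink the dose-1 to dose-2 difference, because the expected-date rule concerns dose 2 alone. The documents do not support that. Consenting participants start the dose-1 survey at once, with no minimum interval since that dose, and no minimum is stated for the booster survey either. Early answers are possible at every dose.

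The rates are also Moderna's, whereas the Statistical Methods analyse mRNA doses together. For Pfizer the background gives only unsolicited counts (64 vs 6), without denominators or a split by dose. Its onset wording makes day 2 a firm lower bound for Moderna only. The vaccine mix is not stated.

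**Conclusion.** The point holds as a minor one. Followed as written, the rule invites between-dose enrollees before the stated Moderna onset, and neither the procedures nor the Statistical Methods describe a safeguard against an early completed answer. Prompt answers may under-record dose-2 swelling and truncate its duration. The size is unknown and possibly negligible. Under the assumptions above, it outweighs sampling error in the dose-2 rate only if this group supplies a sizeable share of dose-2 reports. Any effect on the dose-1 to dose-2 difference depends on dose-1 reports being more complete than dose-2 reports.

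Two further inferences go too far. One is that Hypothesis 2 would be wrongly rejected. The Statistical Methods plan no test against a fixed 16.0%, and this study uses self-report whereas the background rates came from clinical assessment, so the net direction against the general population is uncertain. The other is that patients with missed swelling lose access to arm measurements. The protocol says: "All participants are aware that arm measurements remain available to them as they have in the past".

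**What to change.** **For data already collected (the main remedy, since the Statistical Methods are in the past tense).** Where dose dates were captured:

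- Tabulate days from dose to REDCap completion for every dose, and identify the between-dose enrollees.
- Report swelling frequency and the dose comparison with and without responses given within 7 days of the dose.
- State whether a later dose-2 answer replaced an earlier one.
- Where an ongoing status or end date was recorded, treat effects ongoing at response as censored and estimate median duration by Kaplan-Meier. Otherwise state the limitation.

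If dose dates were not captured, state that response timing could not be checked.

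**For any dose survey still to be sent.** Trigger the invitation from the actual dose date, after an interval that covers the stated onset and most of the stated duration, or re-ask early responders. Under the mean-10-day assumption, four weeks would cover about 92% of episodes.

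**Cost.** One tabulation and one sensitivity analysis, with no new patient contact for data in hand. The sensitivity analysis will have fewer records (number not known), and a later survey means slightly longer recall.
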